3.3. Secondary Objectives

- To determine the feasibility of successful mobilization of autologous stem cells (i.e., minimum of 2×10^6 CD34+ cells/kg should be collected) to be used for ASCT (if applicable).
- To determine toxicities associated with C-R-ICE salvage therapy.
- To determine the TTP, PFS, and OS followed by ASCT (if applicable); Disease-free survival in CR patients.
- To determine the pharmacokinetics/pharmacodynamics relationship between carfilzomib's degree of proteasome inhibition and response rate along with the time course of thrombocytopenia.
- To study differences in clinical outcomes between GCB and non-GCB relapsed/refractory DLBCL following therapy with carfilzomib and R-ICE.

[figure not shown]
Correlative translational research studies to include: phenotypic/genotypic analysis and functional activity (i.e., ADCC and CMC) of patient's peripheral blood mononuclear "effector" cells (PBMC), as well as ex vivo analysis of sensitivity of primary tumor cells to various combinations of carfilzomib versus Bortezomib +/- rituximab; enzymatic assay for chymotrypsin-like activity to determine the degree of proteasome inhibition in primary DLBCL patient samples and patient PBMC specimens; explorative analysis to identify potential factors predictive of response to therapy will be performed (as part of an NIH-supported R01 grant: R01 CA136907-0A1; PI: [name]).

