13.1.2 Phase Ib

The sample size calculation for the Phase Ib population is based on testing the hypotheses concerning the proportion of the population who experience an objective response (i.e., CR or PR) described above. This design requires a total of up to 30 patients in order to achieve approximately 80.1% power to detect differences of 20 percentage points (50% versus 70%).

Based on the excellent response observed in the patients treated in the Phase I portion (ORR 90%) and budget changes, the sample size for the Phase Ib portion was reduced. The phase Ib portion will include 9 additional patients. The efficacy analysis will include evaluable patients in the Phase I and Phase Ib portions combined (sample size up to 45). The sample size calculation for the efficacy analyses is based on testing the hypotheses concerning the proportion of the population who experience an objective response (i.e., CR or PR) described above. This design requires a total of up to 30 patients in order to achieve approximately 80.1% power to detect differences of 20 percentage points (50% versus 70%).

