13.5.2 Phase Ib Decision Rules

Let π represent the proportion of the evaluable population of interest who experience an overall response within 3 weeks after completion of therapy (i.e., 3 cycles) at the carfilzomib MTD. If the response rate of less than 50% is considered unacceptable. A response rate of more than 70% is considered promising and evidence of such will deem the treatment worthy of further study. The null and alternative hypotheses corresponding to the design are

$$H_0 : \pi \leq 50\%,$$
$$H_a : \pi > 50\%.$$

A total of up to 30 evaluable patients will be accrued in the Phase I and Phase Ib portions of the study. The evaluable population is defined as patients who meet eligibility requirements and complete at least 1 cycle of therapy. Unevaluable patients will be replaced.

With this re-design, the probability is 4.8% of falsely concluding that the proportion of those who experience an overall response exceeds 50% and 80.1% is the probability of correctly concluding efficacy when the overall response rate is 70%.

In the event that the actual first stage sample size is not as planned, the adjustment of the first-stage stopping rule will be based on the approximate minimax rule proposed in Green and Dahlberg (1992): Stop the trial if the number of responses is α or less, where α is the largest value for which power properties would be maintained given the attained first-stage sample size, assuming the planned final sample size is achieved and one applies the planned final boundary. If the planned second stage sample size is not attained, the bound will be adjusted so to preserve Type I error.

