13.5.3 Secondary Analyses

Both efficacy and toxicity rates will be estimated using simple relative frequencies. The corresponding 95% confidence intervals for the estimated probabilities will be computed using the method proposed in Clopper and Pearson (1934). The relationship between binary outcomes and collected demographic and baseline variables will be statistically assessed using logistic regression in an exploratory fashion. Maximum likelihood estimation will be utilized in the model fitting procedures as implemented by SAS PROC LOGISTIC. Wald tests of the model effects will be performed to assess statistical significance; see SAS documentation for details. See Hosmer and Lemeshow (2000) for a discussion of such techniques. Alternative parametric models will be considered if model fit is found to be inadequate.

The estimated distributions of overall and progression free survival will be obtained using the Kaplan-Meier method. Estimates of quantities such as median survival will be obtained. Corresponding confidence intervals using the methodology of Brookmeyer and Crowley (1982) will be computed. It is assumed a priori that any drop out times will be non-informative in terms of the censoring mechanism. Groups defined by levels of categorical or dichotomized numeric demographic/baseline variables will be compared in regards to time-to-event distributions using the log-rank test. Cox proportional hazards model regression will be utilized for multivariate analyses.

All tests will be two-sided and tested at a 0.05 nominal significance level. Standard diagnostic plots will be used to assess model fit and transformations of variables may be considered in order to meet statistical assumptions.

The analysis will be performed using the SAS® statistical software system.

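### Splitting numeric baseline variables in two for the log-rank comparisons wastes information in those secondary tests, and no cut-points are set in advance

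*Combined protocol and SAP*

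**What the plan says.** The time-to-event paragraph of section 13.5.3 (Secondary Analyses) covers overall and progression-free survival. Its univariable comparison is: "Groups defined by levels of categorical or dichotomized numeric demographic/baseline variables will be compared in regards to time-to-event distributions using the log-rank test". The next sentence is "Cox proportional hazards model regression will be utilized for multivariate analyses", and it does not say how numeric covariates will be coded. The section then states: "All tests will be two-sided and tested at a 0.05 nominal significance level". It adds that "transformations of variables may be considered in order to meet statistical assumptions".

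The section names no variables to be split, no thresholds and no rule for setting them. Binary outcomes are handled differently: their relationship with baseline variables is to be "statistically assessed using logistic regression in an exploratory fashion", and splitting is not mentioned there.

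On numbers, section 13.5.2 says "A total of up to 30 evaluable patients will be accrued in the Phase I and Phase Ib portions of the study", while section 13.1.2 also gives "sample size up to 45" for the combined efficacy analysis.

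**The concern.** Cutting a numeric variable in two treats every patient on one side of the cut as alike. When risk changes steadily with the variable, the test loses power that the same patients could have provided. With about 30 patients, and fewer events, there is little to spare.

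The missing cut-point rule leaves a second opening. A threshold fixed beforehand gives a valid test. A threshold found by looking for the best separation does not, yet its p-value would be read against the same 0.05. The text neither plans this nor rules it out.

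What is at stake is modest: a real prognostic factor missed, or a spurious one carried into the design of a later trial. Section 13 gives the planning of later comparative trials as the purpose of the analyses.

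**Working it through.** **Plan's own figure.** There is none for these comparisons: no event count, hazard ratio or power. The 4.8% and 80.1% in section 13.5.2 belong to the response-rate test.

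**Inputs.** From the documents: log-rank on split variables, two-sided 0.05 (13.5.3), up to 30 patients (13.5.2). Assumed: covariate distribution, shape and size of effect, number of events, censoring.

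**1. Information kept by a split.** For a normal covariate with a linear log-hazard effect, cut at quantile q, the efficiency relative to the continuous covariate is E = φ(z_q)² / [q(1 − q)].

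| Split | φ(z_q) | E | Loss |
|---|---|---|---|
| 50/50 | 0.399 | 0.159/0.25 = 0.637 (= 2/π) | 36% |
| 30/70 | 0.348 | 0.121/0.21 = 0.576 | 42% |
| 20/80 | 0.280 | 0.078/0.16 = 0.490 | 51% |
| 10/90 | 0.175 | 0.031/0.09 = 0.342 | 66% |

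For a uniform covariate cut at its median, E is the squared correlation between the variable and the half indicator: (1/8)² / [(1/12)(1/4)] = 0.75, a loss of 25%.

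So at a median split of a normal covariate, 30 events would act like 30 × 0.637 = 19, and 18 events like 18 × 0.637 = 11.

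**2. Power, by simulation.** n = 30, normal covariate, two-sided 0.05; Cox score test on the continuous variable against the log-rank test at the sample median.

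| True effect | Events | Continuous | Median split |
|---|---|---|---|
| Linear, HR 2 per SD | about 17–18 | 74–76% | 52–55% |
| Linear, HR 1.65 per SD (log HR 0.5) | about 20 | 52% | 35% |
| Linear, HR 1.65 per SD | 30 | 67% | 48% |
| Linear, HR 1.5 per SD | about 18 | 36% | 25% |
| Step at population median, HR 3 | about 18 | 42% | 48% |
| Step at population median, HR 4 | about 18 | 60% | 66% |

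The ranges in the first row span repeated runs.

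**3. False-positive rate, by simulation.** No true effect, n = 30, 15–30 events, nominal 0.05.

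- Continuous test: 5–6%.
- Split fixed at the median: 5–6%.
- Best cut searched over the central 50% of the data: 24–26%.
- Best cut searched over the central 60%: about 28–32%.
- Best cut searched over the central 80%: 41–45%.

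With 45 patients the three best-cut rates are 25–26%, 31–32% and 40–42%, so the conflict between 30 and 45 does not matter here.

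**The case against.** Several stronger readings are tempting, and the documents do not support them.

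- **That the trial as a whole loses a third of its information.** It does not. Only univariable log-rank tests of numeric variables are touched. The response-rate test, its exact intervals, the Kaplan-Meier curves and the logistic models stand as they are.
- **That the plan inflates false positives.** Section 13.5.3 never says thresholds will be chosen from outcomes. A median or an established clinical threshold, set beforehand, keeps the error rate near nominal. The 24–45% is conditional on a practice that the text leaves open.
- **That particular variables will be cut.** The study calendar collects LDH, beta-2-microglobulin, albumin and blood counts, and age is an eligibility item, but 13.5.3 names none of them as a variable to split.
- **That section 3.3 extends the problem to response.** The objective there, "explorative analysis to identify potential factors predictive of response to therapy will be performed", concerns response. That is a binary outcome and goes to logistic regression, with no splitting mentioned.

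The best defence on substance has three parts. Cox regression is already planned, and nothing stops numeric covariates entering it uncut. If risk truly jumps at the cut, the split is the better test, as the step rows show, and its advantage grows as the cut comes closer to the step. At moderate effects both tests are weak, so the number of events is the main limit. All three are fair. The first does not change the stated univariable method. The second needs a step near the chosen cut, which nothing in the plan leads one to expect. The third limits the size of the gain but does not remove it. The plan's exploratory label is attached to the logistic models, not to these log-rank tests, but the tests are secondary and no decision rule depends on them.

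**Conclusion.** The point holds within a narrow scope and is minor. For numeric baseline variables, section 13.5.3 states a univariable method that is usually less powerful than one the trial can already run, and it leaves the cut-points open. The 36% loss rests on a median cut, a normal covariate and a linear log-hazard effect; other plausible cuts and distributions give 25–66%. The drop of about 20 percentage points in power at a hazard ratio of 2 per SD, and about 11 at 1.5, also rests on an assumed 17–18 events in 30 patients. Type I error is threatened only if cuts are chosen from the outcomes, which the plan does not say. No primary conclusion or dose decision is affected.

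**What to change.** Replace the log-rank sentence in section 13.5.3 with wording along these lines:

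> Numeric baseline variables will be tested as continuous terms in univariable Cox models, log-transformed if skewed. Naturally categorical factors, such as GCB versus non-GCB, will be compared with the log-rank test. Numeric variables will be grouped only for Kaplan-Meier display, at thresholds listed before outcome data are examined.

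State also that numeric covariates stay continuous in the multivariable Cox models.

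The cost is a few lines of text. Cox regression and SAS are already in the plan, and no further patients or data are needed. There are two downsides: some power is lost if the true effect is a step at the cut, and the test relies on a roughly linear log-hazard. The diagnostic plots and transformations that the section already provides for can check the second.

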13.5.1 Historical Control

Patients in this population defined by the eligibility criteria receive standard-of-care which consist of blood product support as needed and growth factor support with each cycle. Based on provided historical information, the overall response rate in this patient population receiving standard-of-care is 50%. It is anticipated that treatment with carfilzomib added to standard R-ICE will increase the overall response rate beyond the clinically significant rate of 70%.

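### Section 13.5.2 prints no response cut-off, states error and power that 30 patients cannot deliver, and ties success to a 70% rate that its test does not assess

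*Combined protocol and SAP*

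**What the plan says.** Section 13.5.1 takes as its benchmark that "the overall response rate in this patient population receiving standard-of-care is 50"%. Section 13.5.2 tests a null of at most 50% against an alternative above 50%, so the primary test is one-sided. For the re-designed study it states that "the probability is 4.8% of falsely concluding that the proportion of those who experience an overall response exceeds 50"%, and that "80.1% is the probability of correctly concluding efficacy when the overall response rate is 70"%. The sample is given in the same section: "A total of up to 30 evaluable patients will be accrued in the Phase I and Phase Ib portions of the study". The synopsis (Statistical Analysis) and section 13.1.2 repeat the 80.1% for up to 30 patients. Section 13.1.2 also gives a combined efficacy sample of up to 45.

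The criterion for going further is worded differently from the test: "A response rate of more than 70% is considered promising and evidence of such will deem the treatment worthy of further study". Section 13.5.2 ends with rules for adjusting a first-stage stopping rule and a planned final boundary, but neither is stated. No section gives a critical number of responses.

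Section 13.5.3, Secondary Analyses, specifies 95% Clopper-Pearson intervals for efficacy and toxicity rates, then Wald tests, log-rank tests and Cox models, and closes with "All tests will be two-sided and tested at a 0.05 nominal significance level".

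**The concern.** A reader who wants to know how many responses make the trial positive cannot look it up. Nor can the number be recovered from the stated error and power, because those figures do not belong to 30 patients. Two other sentences pull in different directions: one asks for evidence above 70%, and one makes every test two-sided. According to sections 13.1.2 and 13.5, the sample was reduced and the Phase I patients pooled after a 90% response rate had been seen. After a change of that kind, the success rule should be a single printed number.

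**Working it through.** **Inputs.** Null rate 50% (13.5.1, 13.5.2); design alternative 70% (13.1.2, 13.5.2); one-sided alternative (13.5.2); n = 30 evaluable (13.5.2); claimed error 4.8% and power 80.1% (13.5.2).

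**Formula.** For the rule *success if X ≥ r*, with X binomial(30, p): error = P(X ≥ r | 0.5) and power = P(X ≥ r | 0.7).

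| r of 30 | Error at 50% | Power at 70% | Two-sided exact p | 95% Clopper-Pearson interval |
|---|---|---|---|---|
| 19 | 10.02% | 84.1% | 0.2005 | 43.9% to 80.1% |
| 20 | 4.94% | 73.0% | 0.0987 | 47.2% to 82.7% |
| 21 | 2.14% | 58.9% | 0.0428 | 50.6% to 85.3% |
| 22 | 0.81% | 43.2% | 0.0161 | 54.1% to 87.7% |

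**Reproducing the plan's figures at n = 30.** No row gives 4.8%/80.1%. The best one-sided rule at 0.05 is r = 20. Lowering the cut-off to 19 takes power past 80% but doubles the error to 10.0%.

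No other test helps. The most powerful randomised test at exactly 5% rejects at 20 or more, and at 19 with probability g = (0.05 − 0.0494)/(0.1002 − 0.0494), about 0.012. Its power is 0.7304 + g × (0.8407 − 0.7304), about 73.2%. That is the ceiling for any test on at most 30 patients at this level, staged or not. Approximations do not reach 80.1% either: one-sided normal formulas give 72.4% (null variance) or 77.2% (alternative variance), and arcsine gives 72.9%.

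**Other sample sizes.** At n = 45 the one-sided rule is at least 29, with error 3.6% and power 83.6%, so 45 does not reproduce the pair. A search of two-stage designs with a futility stop and 28 to 45 patients used

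P(success) = Σ over x > a of P(X₁ = x) × P(X₂ ≥ r − x),

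where a is the first-stage stopping bound. Two designs match, both with 37 patients:

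- stop if at most 12 of 23, success if at least 24 of 37: error 4.82%, power 80.11%;
- stop if at most 18 of 31, success if at least 24 of 37: error 4.79%, power 80.08%.

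Both are one-sided.

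**The 70% wording.** With 20 or 21 responders (66.7% or 70.0%) the one-sided test rejects 50%, yet the observed rate is not above 70%. At a true 70% this happens with probability 0.7304 − 0.4315 = 29.9%. Formal evidence against 70% at one-sided 0.05 would need at least 26 of 30, because P(X ≥ 26 | 0.7) = 3.0% while P(X ≥ 25 | 0.7) = 7.7%.

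**The two-sided sentence.** Applied to the primary test, it requires p ≤ 0.05 two-sided, so the cut-off becomes 21 and power 58.9%. The one- and two-sided readings differ only at exactly 20 responders, which has probability 0.7304 − 0.5888 = 14.2% at a true 70%.

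**The case against.** The strongest reply is that the plan has one primary test. Section 13.5.2 fixes its direction and its error. The two-sided sentence closes a section headed Secondary Analyses, after the Wald, log-rank and Cox methods and next to model diagnostics, so it most naturally covers those. The specific primary rule governs, and even the contrary reading moves the cut-off by one patient. This stands, and it makes the sidedness issue a matter of clarification.

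A reader might infer that the plan contains three competing success thresholds: 20, 21 and 22 of 30. The documents do not support that. They print no threshold, and 22 is only one reading of loose wording about 70%. A formal reading would give 26. Elsewhere in the statistical sections 70% is the rate at which power is calculated.

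Pairing a one-sided 5% test with a descriptive 95% interval is common practice. At 20 of 30 the interval includes 50% although the test rejects it, but nothing makes the interval a decision rule. This also stands.

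The practical reach of the one-patient difference may be small. If the 90% reported for Phase I is assumed to mean 13 or 14 responders among the first 15 patients, finishing on exactly 20 of 30 needs 7 or 6 responders among the other 15. At a true 70% those have probabilities of about 3.5% and 1.2%.

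Finally, printing 20 of 30 at once would settle by wording what is a design decision, while 45 patients and two stages are still in the text. That is right, and it sets the order of the fix. None of these points rescues 80.1% at 30 patients, supplies the missing cut-off, or makes a test of 50% into evidence above 70%.

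**Conclusion.** The point holds as a defect in the stated decision rule. The 4.8%/80.1% attributed to up to 30 patients is wrong as written: at 30 the best one-sided exact rule gives 4.9% error and 73.0% power, a shortfall of about 7 percentage points. The cut-off is missing, and the 70% sentence asks for something the primary test does not assess. The scope of the two-sided sentence is a lesser ambiguity, worth one patient (20 against 21) and a fall in power from 73.0% to 58.9% if it were applied to the primary test.

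These figures assume exactly 30 evaluable patients, independent responses with a common rate, and a single-stage exact binomial test. The link to a 37-patient two-stage design is a numerical match; the documents do not state where the figures came from.

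**What to change.** 1. In section 13.5.2, first settle the final sample size (30, against the 45 in section 13.1.2). Then either define the two stages or delete the leftover stage-adjustment text.
2. Print one one-sided exact binomial rule with its critical number, actual error and actual power. For a single stage of 30: reject the null if at least 20 respond; error 4.9%, power 73.0% at 70%.
3. Correct the 80.1% in the synopsis, section 13.1.2 (where it appears twice) and section 13.5.2, and the 4.8% in section 13.5.2.
4. In section 13.5.2, replace *evidence of such* with rejection of the null hypothesis. State that 70% is the design alternative and that the test does not demonstrate it.
5. In section 13.5.3, limit the two-sided 0.05 sentence to secondary and exploratory tests. Optionally, report a 90% Clopper-Pearson interval beside the primary test. Its lower limit is the one-sided 95% bound, 50.06% at 20 of 30, so interval and test agree.

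Step 1 is a design decision; the rest is wording. The cost is that the stated power falls to what 30 patients provide.

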14 CORRELATIVE STUDIES

14.1 Immune Biomarker Analysis

14.1.1 Blood

- Phenotypic Studies by direct flow cytometric analysis of neutrophils, NK and monocytes for the expression of CD11b/CD18; CD32, CD33, CD62, CD64, CD69, and

CD56 vFunctional Assays in vitro. (1) 10 ml green top – same day as lymph node biopsy

- Antibody-dependent cellular cytotoxicity (ADCC) assays: The capacity to lyse autologous tumor cells in the presence of RITUXAN by peripheral blood mononuclear cells of each patient will be studied by standardized assays, including appropriate controls. (4) 10 ml green tops – same day as lymph node biopsy
- Complement mediated cytotoxicity (CMC) assays: The capacity to lyse autologous tumor cells in the presence of RITUXAN by serum from each patient will be studied by standardized assays, including appropriate controls. (1) gold top – same day as lymph node biopsy
- Genotypic Analysis: Polymorphisms in the IgG Fc receptor FcγIIIa gene will be performed using a nested PCR followed by allele-specific restriction enzyme digestion performed in Roswell Park Department of Medicine Lymphoma/Myeloma Laboratory.(1) 10 ml lavender top – same day as lymph node biopsy
- Assay for proteasome inhibition of patient-derived primary DBLCL cells and PBMCs will be performed using an enzymatic assay for chymotrypsin-like activity. (1) 10 ml green top with each designated time point in Cycle 1 (see section 14.2)

